2.5.9 Training of Staff

Minimal staff training will be required for this study. Recruiting Audiologists will be briefed in the aims and methods of the study. They will be advised as to the inclusion and exclusion criteria in order to enable identification and recruitment of potential participants. They will be informed of the need to maintain participant confidentiality. The Principal Investigator and Research Audiologists will undertake refresher training in the use of speech and cognitive tests.

2.6 Data Collection

2.6.1 Extraction of Data

Data extracted from the patient management system (Auditbase) and completed assessments and questionnaires will be entered into an Excel spreadsheet. The data to be collected is shown in Table 2. Anonymised data, accessible only by the research team, will be stored for five years following completion of the project. The project will be completed once the last participant has carried out their final appointment.

2.6.2 Measured Outcomes and Data Analysis

An ANCOVA will be used to assess any main effects of time or group on participants' performance on the QuickSIN, HHIE, Glasgow disability, MCRM or dual-task performance using initial performance on the QuickSIN as a covariate.

Table 2 Data to be collected during study

Data	Source
Age	At initial appointment from Auditbase
Gender	At initial appointment from Auditbase
Four-frequency average hearing levels	At initial appointment from Auditbase
Number of hearing aids (plus aided ear if	At initial appointment from Auditbase
unilateral fitting)	
Average hours of hearing aid use per day	At initial appointment from Auditbase
Initial HHIE	At initial appointment
Initial Glasgow disability	At initial appointment
Initial QuickSIN SNR loss	At initial appointment
Initial MCRM score	At initial appointment
Initial single task sore	At initial appointment
Initial dual task score	At initial appointment
Final HHIE	At final appointment
Final Glasgow disability	At final appointment
Final QuickSIN SNR loss	At final appointment
Final MCRM score	At final appointment
Final single task score	At final appointment
Final dual task score	At final appointment
Compliance	At final appointment from training diary

3 Project Considerations

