2.5.2 Sample Size

Based on the research design below an a priori sample size calculation has been carried out using the reported effect size of 0.8 on the QuickSIN from Olson et al. (2013). An effect size of 0.8 indicated that 25 participants are needed in each group to give a power of 80% at 5% significance.

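### Four secondary outcomes are adjusted for initial QuickSIN although their own initial scores are collected, which costs precision; the treatment contrast should be settled in the same edit

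*Protocol*

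**What the plan says.** Section 2.6.2 gives the whole analysis in one sentence. It opens "An ANCOVA will be used to assess any main effects of time or group on participants' performance on the QuickSIN, HHIE, Glasgow disability, MCRM or"; the fifth and last outcome in its list is the dual task. It closes "using initial performance on the QuickSIN as a covariate". No other covariate is named.

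Table 2, in the same section, lists "Initial QuickSIN SNR loss" and also "Initial Glasgow disability", "Initial MCRM score" and "Initial dual task score", together with initial HHIE and the initial single-task score. The matching final scores are listed too, so every outcome has its own before and after value.

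Section 2.1 makes speech intelligibility in noise the primary aim; self-report and cognitive tasks come under the secondary aim. Section 2.5.2 sizes the trial "using the reported effect size of 0.8 on the QuickSIN" and concludes that "25 participants are needed in each group to give a power of 80% at 5% significance". Section 2.5.3 stratifies the randomisation by age and sex only.

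**The concern.** In an ANCOVA the covariate earns its place by explaining variation in the final score. For most measures the best single candidate is the same measure taken at baseline. The plan does this for QuickSIN, but carries the QuickSIN baseline over to four other instruments: a handicap questionnaire, a single disability item, a competing-speech threshold and a listening-and-memory task. Where initial QuickSIN predicts these less well than their own initial scores do, confidence intervals on the secondary outcomes are wider than they need be, in a trial of only 25 per arm.

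The protocol names the covariate explicitly. This is therefore a stated choice and not a detail left to a statistical analysis plan; a plan that followed the protocol would inherit it.

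**Working it through.** **The plan's own figure.** With a standardised effect of 0.8, two-sided 5% and 80% power, the normal approximation gives n = 2 × (1.960 + 0.842)² / 0.8² = 24.5, so 25 per group. The stated figure reproduces (power 80.7% by this approximation, 79.1% by the noncentral t). It concerns QuickSIN and uses no baseline adjustment, so the covariate question does not touch it.

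**Inputs for the four secondary outcomes.** The protocol gives n = 25 per arm. It gives no correlations, so two are assumed: r, between an outcome's initial and final scores, and q, between initial QuickSIN and that outcome's final score.

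**Reading A: the final score is compared between groups.** As a share of the final-score variance, the residual is 1 − q² under the plan and 1 − r² with the outcome's own baseline. The planned standard error is larger by the factor √[(1 − q²)/(1 − r²)]. With q = 0.3, 1 − q² = 0.91. Power is for an illustrative 0.5 SD effect (not a protocol figure), by normal approximation.

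| r | 1 − r² | SE factor | Information lost, 1 − (1 − r²)/0.91 | Power: plan vs own baseline |
|---|---|---|---|---|
| 0.5 | 0.75 | √(0.91/0.75) = 1.10 | 18% | 46% vs 53% |
| 0.7 | 0.51 | √(0.91/0.51) = 1.34 | 44% | 46% vs 70% |
| 0.8 | 0.36 | √(0.91/0.36) = 1.59 | 60% | 46% vs 84% |

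Sensitivity to q at r = 0.7: the excess in standard error is 37% at q = 0.2, 34% at q = 0.3 and 21% at q = 0.5. If q = r there is no loss. If q exceeded r, QuickSIN would be the better covariate.

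**Reading B: change is compared between groups.** If time is a model factor, initial and final scores both enter as responses, and the group-by-time contrast is a difference in change. Its variance is 2(1 − r), assuming that initial QuickSIN does not help to predict change. Own-baseline ANCOVA has variance 1 − r² = (1 − r)(1 + r), a fraction (1 + r)/2 of that. So 25 per arm with own-baseline ANCOVA is worth 25 × 2/(1 + r) per arm:

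- r = 0.5: 50/1.5 = 33 (planned SE √(1/0.75), 15% larger)
- r = 0.7: 50/1.7 = 29 (√(1/0.85), 8% larger)
- r = 0.8: 50/1.8 = 28 (√(1/0.90), 5% larger)

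For comparison, Reading A with q = 0.3 gives 25 × 0.91/(1 − r²) = 30, 45 and 63 per arm. Reading B thus gives a much smaller loss at 0.7 and 0.8, but not at 0.5, where it is slightly larger. The two readings cross where 2(1 − r) = 0.91, at r of about 0.55.

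**Reading C: a literal group main effect over both visits.** Averaging the two visits halves the treatment effect, because the groups do not differ by treatment at the first visit. The variance of the average is (1 + r)/2. At r = 0.7 and a 0.5 SD effect, power is about 16%, against 70% for own-baseline ANCOVA.

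**The case against.** The strongest reply is that the sentence also mentions time. A time effect needs both scores as responses, so each outcome's own baseline may already be in the model. The hypotheses in section 2.4 likewise speak of improvements being greater in one group. This stands in part: under the change reading the loss is modest at the higher correlations. It does not make the plan sound. The sentence names main effects and not the group-by-time contrast, own-baseline ANCOVA is still at least as precise as the change comparison, and for QuickSIN itself the initial score would then be both response and covariate.

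A second reply is that no correlation is given, and that the gap between r and q may be narrow for some outcomes. Section 2.2.5.1 describes the MCRM as a speech-intelligibility measure, close in kind to QuickSIN. Glasgow disability is one five-category item, and the MCRM threshold averages only two reversals (section 2.5.8), so high pre-post correlations cannot be taken for granted. This stands, and is why the size is given as a range.

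Three stronger inferences are tempting but not supported:

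- *No outcome has its own baseline.* QuickSIN does, so the covariate choice leaves the primary measure and the sample size alone.
- *Most of the precision is lost.* With q = 0.3, more than half the information is lost only if 1 − r² is below 0.455, that is r above about 0.74. Nothing in the protocol establishes that.
- *Chance baseline imbalance biases the result.* A chance difference has an SD of √(2/25) = 0.28 SD at 25 per arm, but the estimate stays unbiased under randomisation. The imbalance is already part of the wider standard error and is not a second harm.

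**Conclusion.** The point holds for the four secondary outcomes, as an avoidable loss of efficiency. Its size depends on unknown correlations and on which contrast is meant. For a final-score comparison with q = 0.3, standard errors are about 10% to 59% larger than necessary for r from 0.5 to 0.8, and no larger if q equals r. For a comparison of change the excess is about 5% to 15% over the same range. The direction favours the own baseline whenever r exceeds q, which is likely for most of these measures but cannot be shown from the protocol.

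Because validity is intact and the affected outcomes are secondary, this is a should-fix and a free improvement, not a defect that endangers the trial.

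**What to change.** Replace the analysis sentence in section 2.6.2 with wording to this effect: each outcome's final score will be analysed by ANCOVA with group as the factor and the initial score of the same outcome as covariate; the treatment effect is the adjusted difference between groups in final score, with its confidence interval.

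Two details belong in the same edit:

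- Drop the reference to main effects of time and group. Changing only the covariate would leave the own baseline as both response and covariate if time stayed in the model.
- For the dual task, section 2.5.8 defines both a summed score and a decrement from the single task. Name the one to be analysed, and use the initial value of that same measure. Table 2 collects what either needs.

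The cost is one rewritten sentence and no new data, visits or participants. It should be made before outcome data are examined, so that the covariates cannot be chosen in the light of results.

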3.1 Benefits

3.1.1 Local Benefits

For the participants involved, if the intervention is shown to be successful they may experience improvements in their ability to understand speech in background noise. This may ultimately improve the quality of their interactions in challenging listening environments and improve their quality of life. There is evidence to suggest that learning from auditory training programmes can generalise to other listening skills (Henshaw and Ferguson, 2013b) and so they may also experience improvement in other communication situations.

Involving the participant's regular communication partner in the training programme may increase their awareness of the difficulties faced by the patient. This in turn could motivate them to use a greater range of hearing tactics in these challenging listening environments, thereby improving the communication experiences of both the patient and themselves.

This study will provide research evidence for the completion of Higher Training Scheme modules and state registration for the Principal Investigator and material for continuing professional development.

Further research based on this study could be used to augment and improve the existing adult rehabilitation programme provided by the Audiology department by providing an additional non-instrumental management option. It could lead to the development of a user-friendly at home training programme for improving speech perception in noise for hearing-impaired or normally hearing listeners.

3.1.2 National and International Benefits

The results from this study could inform the future national use of training programmes as a non-instrumental intervention in audiological rehabilitation. If the programme is found to be effective it could encourage other departments to use at home speech in noise training as an alternative to other more expensive computerised or clinician-led training programmes. It could also be expanded in order to be incorporated into a rehabilitation programme for patients with confirmed or suspected auditory processing disorder, either with normal hearing or with hearing loss. Being patient-led, rather than clinician-led, this programme also ties in with the current national emphasis on patients taking ownership of their condition and being more involved with decisions regarding their treatment.

3.2 Limitations of Study

A limitation of this study is that the potential for bias in the selection of participants. Although all staff will be given training on the inclusion and exclusion criteria there may be variation in the development of each patient's individual management plan by clinicians meaning that needs may not be phrased in a way which could be interpreted as relating to improved speech perception in noise or complex listening situations. The participant sample may also be limited to patients with reasonably high levels of motivation to improve their listening skills and therefore compliance with the training programme may be greater than could be expected for those with low levels of motivation. Motivation has been linked to better outcomes on training programmes (Musiek et al., 2007) and therefore the results of this study could over-estimate the effectiveness of this training intervention for the general patient population.

As the training programme is patient-led, carried out in the patient's home environment, there is limited control from the researcher as to the way that the training is undertaken by individuals. Although instruction is given regarding noise levels etc. the participant's judgment of "comfortable" or "challenging" may differ and this could lead to variability in the application of training programme between individuals.

This study does not include a measure of on-task learning. This relates to any improvements on the training task i.e. listening to their communication partner in the presence of the specific training distractor. On-task training effects are widely reported in the literature and it is therefore likely that similar effects will be shown in the current study, however the research design does not enable inclusion of a measure of on-task learning due to the patient-led, non-computerised, at home approach.

3.3 Ethical Issues

Full ethical approval will be sought from the North Wales Research Ethics Committee (Central and East). Fully informed consent will be obtained from all participants prior to inclusion in the study. Participants will be able to withdraw from the study at any time. All tools used in the study have been previously used in research or clinical practices within Audiology. If the training programme is found to be effective it will be offered to all participants in the control group.

3.4 Risk Limitation

This study has been designed incorporating measures to mitigate any identified risks. Noise exposure will not exceed the maximum daily noise exposure limits (85 dB A for 8 hours) as testing and training will not exceed 30 minutes per day. Noise levels should not exceed 85 dB A during testing and training. Participants will not be exposed to noise levels which they find uncomfortable. Hearing aids will be optimally set using compression and output limiting in order to ensure that output levels do not exceed unsafe limits. The research team will meet regularly to monitor progress and address any unforeseen issues that may threaten to compromise the project or patient care.

3.5 Confidentiality and Data Protection

All data relating to this study will be gathered and stored in line with the Trust Data Protection Policy.

The data will be recorded on Excel spreadsheets and will be analysed using Excel and SPSS. Participants will be issued with a unique project identification number and their study data will be recorded anonymously against this number. A separate Excel spreadsheet cross-referencing the project identification number against their patient identification number will be stored under password protection, accessible only to the research team. All data will be stored on the departmental server under password protection. Patient identifiable information will be stored for 3-6 months after the end of the research project, while anonymised information will be stored for 5 years before being destroyed.

4 Project Management

4.1. Time Scale

Figure 4 gives the proposed timescale for the research project.

4.2 Research Costs

A breakdown of the costs involved in the project, confirmed by the Finance Department, can be found in Table 3. The study has been awarded a BSA Applied Research Grant meeting all costs.

4.3 Impact of Research on Normal Workload

This study forms part of a clinical training programme for the Principal Investigator whose time is externally funded. Therefore, the time spent by the Principal Investigator on this project is not included in the summary of costs.

Data collection is expected to take 100 hours of clinical time. Research Audiologists will be involved in data collection, undertaking three-quarters of the total research appointments (the remaining quarter will be covered by the Principal Investigator). Part of the funding for this research will be used to backfill lost clinical sessions. The cost of the

02/09/13 30/09/13 28/10/13 25/11/13 23/12/13 20/01/14 17/02/14 17/03/14 14/04/14 12/05/14 09/06/14 07/07/14 04/08/14 01/09/14 29/09/14

Figure 4 Gantt chart showing timescale of project

Table 3 Costs involved in the research project

	Cost (£)	Justification
Staff costs	1753.73	 Backfill of clinical time lost through project: Mid-point Band 6 Audiologist, 75 hours x £18.77 including on-costs Mid-point Band 8 Audiologist, 10.5 hours x £32.95 including on-costs As completion forms part of a clinical training programme for the Principal Investigator all time spent on aspects of the project are covered under the terms of the training programme and are therefore not included in the staff costs. NHBRU staff researchers' time is funded by the NIHR.
Materials and consumables	115	Stationary (paper, envelopes etc.): £12.50 Postage: £37.50 Recordable CDs: £40 Voucher for prize draw: £25
Travel	1420	Travel costs for additional journeys undertaken by research participants: 25 participants with 1 additional journey, £10 per journey 25 participants with 2 additional journeys, £10 per journey Travel for meetings between researchers £670
Apparatus and	125	Purchase of QuickSIN
Total	3413.73	

additional workload generated by this study have been included in the above research costs (see Table 3).

